6.1 Inclusion/Exclusion Criteria

Only subjects meeting all of the following **inclusion criteria** will be considered for study inclusion (will be considered for randomization to study treatment):

- 1. Written informed consent obtained from subjects indicating that they understand the purpose of and procedures required for the study and are willing to participate in it
- 2. Subjects scheduled for elective major spinal or cytoreductive PMP surgery with expected major blood loss
- 3. Male or female, aged \geq 18
- 4. No increased bleeding risk as assessed by standard coagulation tests and medical history
- 5. Intra-operative trigger for treatment
 - a. Subjects undergoing spinal surgery: Intra-operative clinically relevant bleeding of approximately 1 L, requiring hemostatic treatment during surgery.
 - Subjects undergoing cytoreductive PMP surgery: Intra-operative prediction of clinically relevant bleeding of > 2 L (approximately 60 minutes after the start of cytoreductive PMP surgery), requiring hemostatic treatment during surgery.

Subjects having any of the following exclusion criteria, either at screening and/or at baseline will not be included in the study (will not be randomized to study treatment):

- 1. Pregnancy or unreliable contraceptive measures or breast feeding (women only)
- 2. Hypersensitivity to proteins of human origin or known hypersensitivity reactions to components of the IMP
- 3. Participation in another clinical study within 30 days before entering the study or during the study and/or previous participation in this study
- 4. Treatment with any fibrinogen concentrate and/or fibrinogen-containing product within 30 days prior to infusion of BT524
- 5. Employee or direct relative of an employee of the Contract Research Organization, the study site, or Biotest
- 6. Inability or lacking motivation to participate in the study
- 7. Medical condition, laboratory finding (e.g., clinically relevant biochemical or hematological findings outside the normal range), or physical exam finding that in the opinion of the investigator precludes participation
- 8. Presence or history of venous/arterial thrombosis or TEE in the preceding 6 months

6.2 Sample Size Considerations

The non-inferiority margin is defined as 150 mL blood loss, as such difference in blood loss after the decision to treat the subjects with IMP is considered as clinically not relevant.

It is assumed that BT524 is non-inferior that means not worse than FFP/cryoprecipitate with a non-inferiority margin of 150 mL in reducing intra-operative blood loss. Assuming a blood loss of about 500 mL in the FFP/cryoprecipitate treatment arm after the decision to treat the subject with IMP until end of surgery, a standard deviation (SD) of 375 mL, a non-inferiority margin of 150 mL, an alpha-level of 2.5% (1-sided) 100 evaluable subjects per treatment arm are needed to demonstrate the non-inferiority of BT524 by using a t-test (equivalence) with 80% power.

Based on the results of the blinded sample size recalculation (see section 6.2.1) the power was reduced from 90% to 80% to allow an increase of the originally assumed SD of 325 mL to 375 mL.

The sample size will be recalculated at the interim analyses as defined in section 10.0. Sample size estimations will be performed using nQuery Advisor Version 4.0 or higher.

With 100 subjects per treatment arm superiority of BT524 can also be tested with a power of > 80% (t-test, alpha=0.05 2-sided, effect size Δ =0.5).

It is expected that approximately 10% of the randomized subjects will not fulfil the criteria to be included in the PPS. Therefore, approx. 220 randomized subjects are required to reach 200 evaluable subjects in the PPS.

6.2.1 Sample Size Recalculation

After 40 subjects had completed the study, the overall mean and SD for the primary efficacy variable intrasurgery blood loss after decision to treat the subject with IMP was derived using blinded aggregate data of all 40 subjects without separating according to treatment.

If the assumed mean and SD blood loss are not reflected in these subjects, then a sample size adjustment had to be considered to ensure that a sufficient number of subjects will be randomized to maintain a power of 90%.

If an adaption of the sample size is intended, this had to be documented in a protocol amendment.

The sample size recalculation was performed. The CSP (version 4.0) and the sample size considerations were updated (see section 6.2). The power was reduced to 80%.

6.3 Data Monitoring

This data monitoring is not an interim analysis because the analysis is performed with all subjects without separating the subjects according to treatment. Therefore, no alpha-adjustment is necessary.

6.4 Randomization

There will be a stratified randomization per surgery type.

Subjects undergoing spine surgery are to be randomized on a 1:1 basis to receive either BT524 or FFP, and subjects undergoing cytoreductive PMP surgery are to be randomized separately on a 1:1 basis to receive either BT524 or cryoprecipitate.

For subjects undergoing spine surgery the randomization will be stratified according to the predictive blood loss: > 1,000 mL to \leq 2,000 mL and > 2,000 mL. The predictive blood loss will be recorded prior surgery.

Randomization of subjects to treatment will occur intra-operatively (predose) when eligibility for the clinical study has been confirmed.

For subjects undergoing spine surgery the following applies:

After an intra-operative blood loss of approximately 1 L, requiring hemostatic treatment (high risk for the need of fibrinogen supplementation with BT524 or FFP) during surgery, the randomization request will be sent to the pharmacy (if applicable). The pharmacy retrieves the randomization code via Interactive Web Response System (IWRS) and provides the prepared IMP to the unblinded anesthesiologist. In case the anesthesiologist retrieves the randomization code via IWRS, the pharmacy will be informed accordingly and can provide the IMP.

For subjects undergoing cytoreductive PMP surgery the following applies:

Randomization of PMP subjects to treatment will occur intra-operatively (pre-dose) when eligibility for the clinical study has been confirmed. Immediately after the prediction of clinically relevant bleeding > 2 L, requiring hemostatic treatment (high risk for the need of fibrinogen supplementation with BT524 or cryoprecipitate) during surgery, the person responsible for randomization will be informed and the randomization request will be sent. The person responsible for randomization retrieves the

randomization code via IWRS and informs the blood bank/pharmacy. BT524 will be delivered to the operating room by the pharmacy. After randomization, BT524 will be prepared in the operating room in accordance with the manufacturer's instructions and administered immediately after reconstitution by the unblinded anesthesiologist.

After randomization, cryoprecipitate will be thawed and prepared for administration by the local blood bank, delivered to the operating room, and administered upon arrival.

In case the anesthesiologist retrieves the randomization code via IWRS, the blood bank/ pharmacy will be informed accordingly and can provide the IMP.

Subject Identification

For the coherent assignment of the study, documents all subjects having signed the informed consent and having entered the screening period will receive a subject number. The subject number comprises a fivedigit number of which the first two digits define the investigational site and the last three digits the subject enrolled at the corresponding site. Subject numbers are assigned consecutively per site. Subject numbers are assigned unique and will not be replaced i.e., in case of a screening failure.

An interactive web/voice response system will be implemented and used for randomization and re-supply. Detailed instructions for the use of IWRS systems are provided in a separate document that will be filed in the Investigator Site File.

The random allocation of treatments to subjects will be done using a computerized randomization program. Subjects will receive a randomization number, which will be recorded along with the date of randomization in the eCRF.

7.0 Study Parameters and Covariates

7.1 Primary Efficacy Parameter

The primary efficacy parameter is determined from the intra-operative blood loss after the decision to treat the subject with IMP until the end of the surgery as measured by the amount of blood from the blood suction unit and the amount of blood from swabs, surgical cloths and compresses. The end of surgery is defined as time of last suture.

7.2 Secondary Parameters

7.2.1 Efficacy

Secondary efficacy will be determined using the following parameters:

- Proportion (%) of subjects with successful correction of fibrinogen level (FIBTEM A10) 15 minutes after start of first IMP administration.
 Successful correction of fibrinogen level in a subject is defined as restoring fibrinogen FIBTEM A10 baseline level to at least 95% measured by ROTEM 15 minutes after start of first IMP administration. A correction of at least 95% is considered successful, as measurement methods has a coefficient of variation of about 5% (Solomon et al., 2015).
- Time to first successful correction of fibrinogen level (15 minutes or 90 minutes after start of first IMP administration, end of surgery, not within surgery).
- Total amount (volume in mL and number of units [bags]) of transfusion products (allogeneic blood products) or autologous blood transfusion infused after start of first IMP administration until end of surgery. The end of surgery is defined as time of last suture.
- Amount (volume in mL and number of units [bags]) of red blood cells (RBCs) (allogeneic and autologous) infused after start of first IMP administration until end of surgery. The end of surgery is defined as time of last suture.

- Post-operative blood loss in the first 24 hours.
- Proportion (%) of subjects with rebleeds after the end of surgery until Day 8. Rebleeds are defined as any bleed requiring hemostatic treatment (including reoperation) after the end of surgery until Day 8.
- Hospital length of stay after surgery, defined as the date of discharge minus the date of surgery.
- In-hospital mortality.

7.2.2 Exploratory Efficacy

Exploratory efficacy endpoints:

Overall Mortality

7.2.3 Safety

Safety and tolerability in this clinical study will be addressed by the following safety parameters:

- Frequency, severity, seriousness and causality of AEs.
- Changes in vital signs (including pulse [heart rate], blood pressure, respiratory rate, body temperature).
- Change in clinical laboratory assessments of hematology, clinical chemistry and urinalysis.
- Change in clinical laboratory assessments of markers of coagulation:

Prothrombin time (PT)/International Normalized Ratio (INR), activated partial thromboplastin time (aPTT), thrombin-antithrombin III complex (TAT), prothrombin fragments 1+2 (F1+2), D-dimer, protein S (PS), protein C (PC), antithrombin III (AT III), thrombin time (TT) and Endogenous Thrombin Potential (ETP) measured by Thrombin Generation Test (TGT) (TGT only for subjects undergoing cytoreductive PMP surgery).

• Change in clinical laboratory assessments of coagulation factors:

Factor II (FII), factor V (FV), factor VII (FVII), factor VIII (FVIII), factor IX (FIX), factor X (FX), factor XI (FXI), factor XIII (FXIII) and von Willebrand factor (vWF) (vWF only for subjects undergoing cytoreductive PMP surgery).

- Frequency, severity, seriousness and causality of thromboses and TEEs, of relevant bleeding complications, of Hypersensitivity/ anaphylactic reactions, and of bleeding related ischaemic events.
- Change in viral status.

7.3 Predetermined Covariates and Prognostic Factors

In addition to treatment as a prognostic factor, there is a predetermined covariate for subjects undergoing spinal surgery only. The stratification factor predicted blood loss (> 1,000 mL to \leq 2,000 mL and > 2,000 mL) is a covariate for the analysis of the primary efficacy variable and two secondary efficacy variables: amount of RBCs infused after IMP, post-operative blood loss in the first 24 hours.

Predicted blood loss will also be used as stratification factor in the analyses of two secondary efficacy variables: proportion of subjects with successful correction of fibrinogen level 15 minutes after start of first IMP administration, proportion of subjects with rebleeds after the end of surgery until Day 8.

8.0 Definitions

8.1 Age

Age will be calculated as:

Age = (date of informed consent – date of birth) / 365.25 rounded to lowest integer

Only year of birth will be recorded. The date will be imputed as 01 January. The imputed date of birth will be used for age calculation.

8.2 Baseline

If not stated otherwise, the last non-missing valid observation prior to surgery will serve as the baseline measurement.

8.3 Change from Baseline

Change from baseline will be calculated by statistical programming as follows:

Change from baseline = Post-baseline measurement – baseline measurement

8.4 Missing Data Conventions

In this short study, not many missing values are expected. Therefore, in general, data will not be imputed.

In case there will be at least 10% missing data, these data will be checked at the Blind Data Review Meeting (BDRM) and imputation methods will be considered. It is assumed that these missing data will be at random and an imputation method which is based on the worst case of the respective treatment group will be used as a sensitivity analysis.

For binary endpoints, an observed case analysis (excluding missing data) will be considered to be the primary analysis method and a non-responder analysis (treating missing values as non-responders or the worst case) may be performed as a sensitivity analysis if deemed necessary.

Imputed values will be flagged in listings.

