8.11 Amount of Blood Loss

During surgery, the blood loss will be quantified by measuring the continuous bleeding mass with a blood suction unit (and/or a cell saver) and by calculation of the amount of blood from swabs, surgical cloths and compresses. For the primary endpoint, the amount of blood will be measured for the time between decision to treat and end of surgery.

Calculation of blood loss:

Blood loss (mL) = Volume of blood on swabs, surgical cloths and compresses (mL) + Volume of blood in the suction container (mL) + Total volume of blood loss from other sources (mL)

Volume of blood on swabs, surgical cloths and compresses (mL) = Weight of used/unused surgical cloths and compresses (g) - Weight of dry swabs, surgical cloths and compresses (g). 1 g weight represents 1mL volume of blood.

Volume of blood in the suction container (mL) = Total volume of fluid collected in suction container (mL) - Total volume of anticoagulant solution in blood suction container (mL)* - Total volume of irrigation solution (mL)

* Not applicable for abdominal surgery

Total volume of irrigation solution = Capacity of irrigation syringe (mL) * Number of times irrigation syringe used

Handling of missing data:

For the calculation of **Blood loss**, Volume of blood on swabs, surgical cloths and compresses and Volume of blood removed from the surgical field by the blood suction is required. If there is at least one missing value (see above for single items needed) the blood loss cannot be calculated, and the volume will be missing.

For the calculation of blood in the suction container: Total volume of anticoagulant solution in blood suction container is not applicable for abdominal surgery and will not be considered for the calculation.

For the calculation of Total volume of irrigation solution: If Capacity of irrigation syringe is missing and Number of times irrigation syringe used > 0 then volume is missing. If Capacity of irrigation syringe is provided and Number of times irrigation syringe used is missing, then volume is missing. If Capacity of irrigation syringe is missing and Number of times irrigation syringe used = 0 then volume is 0.

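### The planned worst-case imputation penalises missing comparator values as well as missing BT524 values, so it is not a reliable stress test of non-inferiority

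*SAP*

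**What the plan says.** SAP section 8.4 leaves data unimputed in general. The exception is introduced by "In case there will be at least 10% missing data": the data then go to the blind data review meeting, where imputation methods are considered. For that case the SAP adds "It is assumed that these missing data will be at random" and, in the same sentence, "an imputation method which is based on the worst case of the respective treatment group will be used as a sensitivity analysis". It does not define the worst case, and it does not say whether the 10% is counted overall, per arm or per endpoint.

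SAP section 8.11 explains how the primary endpoint goes missing: if any required component is absent, "the blood loss cannot be calculated, and the volume will be missing".

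SAP section 12.5.1 places the primary non-inferiority test in the PPS. The sensitivity analyses it lists are a repeat in the FAS and mFAS and an analysis of spinal subjects without tumours. The imputed analysis is not mentioned there and has no analysis set. SAP section 9.4 gives lack of a post-dose primary measurement as an example of a deviation that removes a subject from the PPS. Protocol section 10.5 allows no imputation for the primary endpoint; SAP section 4.1 declares the departure. Neither document specifies a tipping-point or margin-shifted analysis.

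**The concern.** Under missing at random, an unobserved value should resemble the observed values of similar subjects. Setting it to the most extreme value in the arm does not do that.

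The more important problem is direction. Higher blood loss is worse, and non-inferiority requires the upper confidence limit for BT524 minus comparator to lie below 150 mL. A stress test of that claim should make BT524 look worse. This rule also makes the comparator look worse, and so partly or wholly offsets its own penalty. Whether it challenges or flatters BT524 then depends on which arm happens to lose more data. What is at stake is how far a reader can trust the imputed analysis as evidence that a non-inferiority finding survives missing data.

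**Working it through.** **Inputs from SAP section 6.2.** Margin: "The non-inferiority margin is defined as 150 mL blood loss". Spread: "a standard deviation (SD) of 375 mL". Comparator mean: "Assuming a blood loss of about 500 mL in the FFP/cryoprecipitate treatment arm". Error level and size: "an alpha-level of 2.5% (1-sided) 100 evaluable subjects per treatment arm are needed", with 80% power.

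**The plan's own figure.** For a true difference of 0, the noncentral t calculation gives 99 per arm for 80% power (79.97% at 99, 80.4% at 100). The stated 100 per arm is reproduced.

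**Assumptions not in the documents.** Worst case is the largest observed blood loss in the arm. Values are missing completely at random, 20 of 200. The splits between arms are chosen for illustration. Blood loss is normal, gamma or log-normal; the skewed shapes are included because SAP section 4.1 itself allows for non-normal data. The ANOVA covariate is left out.

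**Direction by formula.** Let f be the share missing in an arm, W its worst value and m its observed mean. Then

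shift in (BT524 - comparator) = f_B(W_B - m_B) - f_C(W_C - m_C).

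Take W - m = 1,440 - 500 = 940 mL in both arms, about 2.5 SD (940/375 = 2.51):

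- 7% BT524, 13% comparator missing: (0.07 - 0.13) × 940 = -56 mL, toward BT524.
- 10% each: 0.
- 13% BT524, 7% comparator: +56 mL, against BT524.
- 5% BT524, 15% comparator: -0.10 × 940 = -94 mL, or 94/150 = 63% of the margin. With a worst value of 1,250 mL this is -75 mL; with 2,000 mL, -150 mL.

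**Simulation at a true difference of 150 mL.** 100 per arm; a pass means that the upper 95% limit is below 150 mL. Complete-case analysis passes in about 2.5% of trials throughout. Repeat runs agree to within about 1 percentage point and 2 mL.

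| Missing BT524 / comparator | Pass rate: normal, gamma, log-normal |
|---|---|
| 5 / 15 | 28%, 41%, 46% |
| 7 / 13 | 12%, 19%, 25% |
| 10 / 10 | 1.9%, 3.5%, 6.7% |
| 13 / 7 | under 1% in all three |

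At 7/13 the mean shift is about -55, -81 and -96 mL respectively.

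**Second setting: 110 per arm (the approximately 220 randomised), 22 missing.** Results for normal / log-normal data at a true difference of 150 mL:

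- 8/14: 11% / 25%.
- 11/11: 1.9% / 7.4%.
- 14/8: 0.2% / 1.1%.

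With truly equal arms, complete cases pass in about 80%. The imputed analysis passes in 99% / 93% at 5/17, 69% / 48% at 11/11 and 13% / 7% at 17/5.

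**Does penalising only BT524 help?** At 5/17 and a true difference of 150 mL (normal / log-normal):

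- Worst value of each arm: 36% / 55%.
- BT524 at its mean + 150 mL, comparator at its mean: 2.8% / 3.1%.
- BT524 at its worst value, comparator at its mean: 0.3% / 0.2%.
- Complete case: 2.3% / 2.7%.

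These are single imputations, which understate the standard error; they show direction only.

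**The case against.** Four points on the other side carry weight.

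- **The primary claim does not depend on this analysis.** A reader might infer that the rule inflates the trial's type I error or can manufacture non-inferiority. The documents do not support that: the claim is decided in the PPS, which drops subjects without the endpoint, so imputed values could act only in the FAS or mFAS. If the complete-case and imputed analyses must both pass, the joint false pass rate cannot exceed the complete-case rate of about 2.5%. What remains is a failure to challenge: at 7/13 and 5/15, almost every false complete-case pass also passes the imputed analysis.
- **The rule does not always favour BT524.** With more BT524 values missing it is severe. The direction also holds only on average: at 10 versus 12 missing, the estimate moved against BT524 in 22% (normal) to 36% (log-normal) of trials. If 20 of 200 values are missing purely by chance, a split of 7/13 or worse in that direction has probability 12%, and 5/15 or worse 1.6%. Averaged over chance splits, the pass rate is 4%, 7% and 10% (normal, gamma, log-normal). The documents give no reason to expect more loss in the comparator arm.
- **The trigger may never be reached.** Section 8.11 shows how a value becomes missing, not how often, and section 8.4 expects few missing values. The 10% in section 6.2 is for all PPS exclusions. It would be wrong to infer from these passages that 10% missing is likely.
- **A sensitivity analysis may depart from the base assumption.** The missing-at-random clause could be read as describing the unimputed analysis, which makes the wording ambiguous rather than flatly contradictory. It still leaves no imputation that follows the stated assumption.

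Using the subject's own arm is also not the root fault. A pooled worst value moves the estimate similarly (at 5/17, normal data, equal arms: -112 mL against -101 mL). The fault is penalising missing comparator values at all.

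**Conclusion.** The concern holds as a defect of the sensitivity analysis. The rule is not a missing-at-random method and is not directed at non-inferiority, and its direction depends on which arm loses more data. At a true difference of 150 mL with 20 of 200 values missing, the pass rate runs from under 1% (13/7) through 2-7% (10/10) to 12-25% (7/13), with a shift of about -55 to -96 mL in the last case.

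These sizes rest on reading worst case as the arm maximum and on the assumed splits and distributions. They are pass rates of an analysis that runs only if the trigger is met, not error rates of the trial's conclusion. The point should be corrected before database lock, but it does not undermine the primary analysis.

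**What to change.** In SAP sections 8.4 and 12.5.1, replace the worst-case rule with two analyses, both assigned to the FAS and mFAS, since the PPS drops the subjects concerned:

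1. **Missing-at-random analysis.** Multiple imputation by arm and by surgery type, adding the predicted blood-loss stratum for spinal subjects only, because SAP section 6.4 does not stratify PMP subjects by it.
2. **Tipping-point series.** Add a penalty to the imputed BT524 values only, for example +150 mL and upward, and leave missing comparator values at their missing-at-random imputation. Report the penalty at which non-inferiority is lost.

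If the 10% trigger is kept, state what it is counted over. The cost is SAP wording and a little more programming. The downside for the sponsor is a sensitivity result that may be less favourable to BT524.
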